9.2 Data Analyses/Study Endpoints

Quantitative data will be expressed as mean \pm standard type or median with interquartile range, and categorical variables as counts and frequencies. We will use complete case analysis to manage missing data. All statistical analyses will involve the use of Excel. Descriptive statistics will be used to summarize pain scores and opioid use in the intervention and the historic control group. Average number of opioid pills requested will be compared between the study cohort and the historic control group. A paired t test will be used to compare the difference in average pill count between the two groups based on the matched pairs with historic controls. Confidence intervals for the number of pills and the secondary endpoints of reported pain scores, satisfaction, and length of stay will be calculated in the study cohort and for the historic controls.

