5.2 Use of Opioids

In order to capture medication use related to their injury, including the use of opioids, we will link patient electronic health record (EHR) data to the other data sources using Medical Record Numbers and date of birth. We will collect opioids information using CSLINK. Prescribed opioid medications include: codeine, dihydrocodeine, morphine, hydromorphone, oxymorphone, tapentadol, buprenorphine, methadone, oxycodone, fentanyl, remifentanil, and hydrocodone. Tramadol usage will also be included. We will convert all opioid doses into a single metric using morphine milligram equivalents (MME).

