Patients can pick and choose which visualizations to watch based on their own preferences. In clinical testing, we asked patients to use the headset at least thrice daily, for 15 minutes per treatment period, and to also use as needed for breakthrough pain between treatments. The appliedVR software allows our team to monitor adherence with the therapy, including the visualizations selected by the user, the amount of exposure time, and the time of day the visualization was viewed.

Using Samsung Gear goggles, participants will be shown a short VR experience of swimming with dolphins, lasting approximately 2 minutes. During your pre-op visit, a study staff member will show the participants how to use the VR goggles and connected smartphone and answer any questions about them.

They will be asked to watch VR only once after they wake up after surgery, and any time they feel pain. We recommend taking short, 5-10-minute breaks after 30 minutes of use, but they may continue afterward. This experience is an addition to usual care in the hospital and will not impact any additional care the participants receive at CSMC.

We will also obtain pain ratings, participants' use of pain medication while recovering from the surgery, and any physical symptoms they report to the nurse throughout your stay. Recording all of this information is standard of care. It is not being done for research. We will review medical records to obtain this type of information.

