8.0 STATISTICAL CONSIDERATIONS

8.1 Sample Size

This is an exploratory pilot study to estimate the effect of VR on opioid use during the stay. We will enroll 20 eligible patients to this study. We will include data from 20 patients for the historical control portion of the study matched 1 to 1 on age, surgery type, use of neoadjuvant therapy, and use of paravertebral block analgesia. Assuming a standard deviation of 1, a sample size of 20 matched pairs would produce a confidence interval with a distance from the mean to the limits that is equal to 0.468 for the difference in requested pill count.

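### All opioid doses are converted to MME, but the stated precision, the paired test and the opioid confidence intervals are all for a pill count

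*Combined protocol and SAP*

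**What the plan says.** The primary objective (section 2.0) is to estimate the effect of VR on opioid use. Section 2.2 names the endpoint without a unit, and section 8.1 gives the aim as to "estimate the effect of VR on opioid use during the stay".

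Two measures of opioid use then appear.

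- **MME.** Section 5.2 lists twelve opioids, adds tramadol, does not restrict the data to tablets, and states: "We will convert all opioid doses into a single metric using morphine milligram equivalents (MME"). The term does not appear in sections 2.0, 2.2, 8.1 or 9.2.
- **Pills.** Section 8.1 gives the precision as "0.468 for the difference in requested pill count". Section 9.2 (Data Analyses/Study Endpoints) says "Average number of opioid pills requested will be compared between the study cohort and the historic control group", then "A paired t test will be used to compare the difference in average pill count between the two groups", and then "Confidence intervals for the number of pills and the secondary endpoints", these last to be calculated in each group.

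Section 9.2 has one further opioid analysis, with no stated unit: "Descriptive statistics will be used to summarize pain scores and opioid use in the intervention and the historic control group".

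The stated data source is the medical record. Section 5.2 names CSLINK, sections 5.1.2 and 6.2 name the EHR, section 7.0 refers to record review for "use of pain medication while recovering from the surgery", and section 3.0 says that control data come from the controls' medical records. These sections describe medication used or opioid information in general. None says how a count of pills requested is to be obtained from the record in either group.

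**The concern.** The measure that the plan defines as common to all opioids is not the measure that it tests. A pill count treats a tablet of one drug and strength as equal to a tablet of any other, and it omits doses given in any other form. A count of requests may also differ from a count of doses taken.

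This matters because the comparison is with historical controls operated on between October 2008 and October 2018. The matching factors in sections 3.0 and 8.1 do not include opioid drug, route or calendar year. Nothing in the design therefore makes the opioid mix the same in the two groups. If it differs, the paired pill difference can be larger or smaller than the difference in opioid use, or of opposite sign. In addition, if requests cannot be read directly from the record, staff must settle on a working definition during extraction, and the plan does not ensure that it is the same for both groups.

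**Working it through.** **1. The plan's own figure.** Inputs from section 8.1: 20 matched pairs, SD 1, half-width 0.468. The confidence level is not stated; 95% two-sided is assumed.

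Half-width = t(0.975, 19) × SD of the paired difference / √20 = 2.0930 × 1 / 4.4721 = 0.468.

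The figure reproduces. A 90% paired interval would give 0.387, and two independent groups of 20 with SD 1 would give 0.640. The figure is therefore a paired 95% interval with SD 1 taken as the SD of the within-pair difference. Its unit is pills.

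**2. Where each measure is used.**

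| Item | Variable in the plan |
|---|---|
| Endpoint (2.2) | Opioid use, no unit |
| Metric for doses (5.2) | MME |
| Precision (8.1) | Requested pills |
| Between-group comparison (9.2) | Requested pills |
| Paired t test (9.2) | Average pill count |
| Opioid confidence intervals (9.2) | Number of pills |
| Descriptive summary (9.2) | Opioid use, no unit |

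**3. How mix alone can move a pill count.** For a given total MME, mean pills = MME × (1 − non-tablet share) / MME per tablet. At equal mean MME in the two groups:

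pills VR / pills control = [(1 − non-tablet share VR) / (1 − non-tablet share control)] × (MME per tablet control / MME per tablet VR).

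The documents give none of these inputs. The values below are assumptions that show only how the mechanism works.

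- Non-tablet share 40% in controls and 30, 35, 40, 45 or 50% in VR patients, same tablet strength: 0.70/0.60 = 1.167, 0.65/0.60 = 1.083, 1, 0.55/0.60 = 0.917, 0.50/0.60 = 0.833. The pill difference is +17, +8, 0, −8 or −17% with no difference in MME.
- Control-to-VR ratio of MME per tablet 0.8, 0.9, 1, 1.1 or 1.25, same non-tablet share: −20, −10, 0, +10 or +25%.

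**4. Precision on the MME scale.** Half-width = 0.468 × SD of the paired MME difference. The documents give no such SD. Assumed values of 20, 40 and 60 MME give 0.468 × 20 = 9.4, 0.468 × 40 = 18.7 and 0.468 × 60 = 28.1 MME.

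If only a per-patient SD can be had from the controls, and the SD is equal in both groups, the SD of the paired difference is SD × √(2(1 − ρ)), where ρ is the within-pair correlation. For ρ of 0, 0.25 and 0.5 the half-width is 0.662, 0.573 and 0.468 × the per-patient SD.

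**The case against.** The strongest case for the plan is that a pill count was intended. It recurs in sections 8.1 and 9.2, and it fits an intervention that patients are told to try before they ask for or take an opioid (section 5.1.2). A request is closer to the behaviour that VR is meant to change than a dose total is. The study is also an exploratory pilot with no confirmatory claim. These points stand, and they are a reason to keep the count. They do not remove the need to define it, to say how non-tablet doses are handled, or to give an estimate with an interval for the quantity named in the objective.

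A reader might also infer more than the documents support:

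- **That MME is abandoned.** The descriptive summary of opioid use in section 9.2 may be meant in MME, since section 5.2 is the section on opioid use. No unit is stated, so this is open. Even on that reading, MME has no stated test, interval or precision.
- **That the test and intervals are explicitly for pills requested.** Only section 8.1 and the comparison sentence in section 9.2 say so. It is the natural reading for the test and intervals, but a count of pills taken is not excluded.
- **That the pill count has no data source.** The general source is stated for both groups. What is missing is the step from that record to a count of requests.
- **That 0.468 is an error.** It is correct arithmetic for an SD of 1.
- **That MME is the worse choice because it grows with length of stay.** A pill total over the stay grows in the same way.

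**Conclusion.** The mismatch is established from the text: MME is set as the single metric for opioid doses, while the stated precision, the only paired test and the opioid confidence intervals are for a pill count. How that count is obtained from the record is not stated for either group.

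The effect on the result cannot be sized from the documents. It is zero if drug, strength and route mix are the same in both groups. Under the assumed inputs above it runs from −20% to +25% of the pill count at equal MME, but those inputs have no source in the plan and do not show that the trial's estimate is biased.

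The point should be fixed before data extraction, because the study's purpose is to estimate this one effect. It does not make the trial invalid or change its size.

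**What to change.** - **Sections 2.2 and 9.2:** name total MME per patient from the EHR, over the postoperative hospital stay, as the primary variable. Fix one conversion table, and state the same start and end of the window for both groups.
- **Section 9.2:** apply the paired t test and a 95% confidence interval to the paired MME difference (VR patient minus matched control). State the unit of the descriptive opioid summary. Keep the pill count as a descriptive secondary measure, say whether it means requested or taken, and give its source in each group.
- **Section 8.1:** state that with 20 matched pairs the half-width of the 95% interval is 0.468 × the SD of the paired MME difference, and supply that SD from control data or as a stated range.

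The cost is edits to three sections, a fixed conversion table and one summary of control MME data. EHR extraction and MME conversion are already planned, and the sample size is unchanged. There are two drawbacks. The stated precision will look less favourable and will depend on an SD that the documents do not give, and the request count becomes secondary although it is closer to the behaviour that VR targets. The change puts doses on one scale; it does not remove differences in prescribing between the control period and the VR patients.

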9.0 STUDY MANAGEMENT

9.1 Conflict of Interest

Any reportable conflict of interest will be disclosed to the local IRB and will be outlined in the Informed Consent Form.

9.2 Institutional Review Board (IRB) Approval and Consent

It is expected that the IRB will have the proper representation and function in accordance with federally mandated regulations. The IRB should approve the consent form and protocol.

In obtaining and documenting informed consent, the investigator should comply with the applicable regulatory requirement(s), and should adhere to Good Clinical Practice (GCP) and to ethical principles that have their origin in the Declaration of Helsinki.

Before recruitment and enrollment onto this study, the patient will be given a full explanation of the study and will be given the opportunity to review the consent form. Each consent form must include all the relevant elements currently required by the FDA Regulations and local or state regulations. Once this essential information has been provided to the patient and the investigator is assured that the patient understands the implications of participating in the study, the patient will be asked to give consent to participate in the study by signing an IRB-approved consent form.

Prior to a patient's participation in the trial, the written informed consent form should be signed and personally dated by the patient and by the person who conducted the informed consent discussion.

9.3 Registration Procedures

All subjects that sign informed consent will be assigned a subject number sequentially by their date of consent. Those subjects that do not pass the screening phase will be listed as screen failures on the master list of consented subjects. Eligible subjects, as determined by screening procedures and verified by a treating investigator, will be registered on study at Cedars Sinai Medical Center by the Study Coordinator.

Assignment of Subject ID: The study team will track all subjects who sign consent on a subject screening/enrollment log using a unique screening ID (S001, S002, etc.). Subjects found to be ineligible will be recorded as screen failures.

Eligibility Verification

Prior to registration, all subjects must undergo eligibility verification by the investigators. The following documents will be completed and provided for review:

- Registration form (or equivalent)
- Copy of applicable source documents
- Eligibility checklist (signed by investigator)
- Signed patient consent form and Subject's Bill of Rights
- HIPAA authorization form

Oversight by the principal investigator is required throughout the entire registration process

9.4 Data Management and Quality Control and Reporting

Data will be entered into a HIPAA-compliant database. The Study Staff will be responsible for data processing, in accordance with procedural documentation. Data collected from medical record, such as opioid prescriptions and physician history, will reside on secure CSMC servers and an ID will be assigned to each individual in order to abstract PHI and the medical record number. Each dataset will utilize different unique ID's and a list linking each unique ID to each participant will be stored internally on the secured CSMC network. The linking list allows a researcher with access to the secured files to merge all data using statistical software, while maintaining data confidentiality.

(Researcher should record if patient asked questions while using it)

Do you have any thoughts on how the device can be improved?

VR Experiences:

From what you watched, which did you like the most? Why?

From what you watched, which did you like the least? Why?

What was your favorite part about watching the 'experiences'?

What was your least favorite part about watching the 'experiences'?

What did you think about the duration of the 'experiences'? Were they too long? Too short?

What would be your ideal 'experience' duration? (e.g. how many minutes long would you want them to be)

If at all, how do you think the 'experiences' can be improved?

What would you like to see in additional 'experiences'?

Would you recommend the Virtual Reality to your family and friends?

Perceived Effects of Participation:

[IF ANXIETY IS A CONCERN:] Do you think that wearing the device affected your anxiety level?
[IF YES:] How so?

Do you think that wearing the device affected your pain? [IF YES:] How so?

These are all the questions we have for you today. Is there anything we didn't mention that you would like to discuss?

Thank you again for your participation in this study, and please feel free to contact our research coordinator if you have anything else you would like to discuss with us about this project.

APPENDIX 2

VR Experience Tracking Log

How many times did you watch Virtual Reality	None	Once	Twice	Three times	Four times	More than four times
DATE						
						
						
	
